5.1.3 Dose Limiting Toxicities

For the purpose of guiding decisions regarding dose escalation in Parts 1A, 1B, and 1C, DLTs will be defined based on the incidence, intensity, and duration of AEs excluding toxicities clearly related to disease progression or intercurrent illness. The DLT period will start on the first day of cycle 1 and end at day 28 (therefore, 4 weeks) in Parts 1A, 1B and 1C. The severity of AEs will be graded according to National Cancer Institute (NCI) Common Terminology Criteria for Adverse Events (CTCAE) v5.0.

For the purpose of participant management, DLTs that occur at any time during treatment (not limited to DLT observation period) will result in study drug being held pending evaluation of the event being related to study drug, in accordance with [Section 7.4](#). A participant is considered DLT evaluable if receiving 1 dose of BMS-986315 in Part 1A, 1 dose of BMS-986315 and nivolumab (480mg) in Part 1B, or 1 dose of BMS-986315 and cetuximab (500 mg/m²) in Part 1C, and completing the DLT observation period.

Participants who withdraw from the study during the 4 week DLT evaluation period for reasons other than a DLT may be replaced with a new participant at the same dose level. The incidence of DLT(s) during the 4 week DLT evaluation period will be used in dose escalation decisions and to define the MTD/RP2D in monotherapy and in combination with nivolumab or cetuximab. AEs occurring after the 4-week DLT period will be considered for the purposes of defining the RP2D upon agreement between the Sponsor and Investigators. Participants experiencing a DLT will not be retreated with study drug (except for Grade 3 or 4 acneiform rash in Part 1C), and will enter the safety follow-up period of the study.

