Other \geq Grade 3 toxicity events, excluding toxicities clearly related to disease progression or intercurrent illness, will be considered a DLT, with the exception of the following Grade 3 events which will NOT be considered DLTs:

- Grade 3 electrolyte abnormalities that are not complicated by associated clinical adverse experiences, last less than 72 hours and either resolve spontaneously or respond to conventional medical intervention.
- Grade 3 nausea, vomiting, or diarrhea that lasts less than 48 hours, and either resolves spontaneously or responds to conventional medical intervention.
- Grade 3 elevation of amylase or lipase not associated with clinical or radiographic evidence of pancreatitis.
- Grade 3 fever not associated with hemodynamic compromise (e.g., hypotension, clinical or laboratory evidence of impaired end-organ perfusion).
- Grade 3 endocrinopathy that is well controlled by hormone replacement.
- Grade 3 tumor flare (defined as pain, irritation, or rash that localizes to sites of known or suspected tumor).
- Grade 3 fatigue that lasts \leq 7 days.
- Grade 3 infusion reaction that returns to Grade 1 in $<$ 6 hours.

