- d) Participants with controlled brain metastases are eligible. Controlled brain metastases are defined as no radiographic progression for at least 4 weeks following radiation and/or surgical treatment (or 4 weeks of observation if no intervention is clinically indicated), and no longer taking steroids for at least 2 weeks prior to first dose of study treatment, and with no new or progressive neurological signs and symptoms.

- e) Study participants will be expected to have received standard of care therapies, including an available PD-(L)1 inhibitor known to be effective in the tumor type for which they are being evaluated.
- f) Participants with RCC
 - i) Advanced or metastatic RCC with clear cell component
 - ii) Participants must have received at least 1 but not more than 2 prior anti-angiogenic therapy regimens (including but not limited to sunitinib, sorafenib, pazopanib, axitinib, tivozanib, and bevacizumab) in the advanced or metastatic setting. Prior cytokine therapy (e.g., IL-2 IFN-g), vaccine therapy, or treatment with cytotoxics is allowed.
 - iii) **Not applicable per revised protocol 02:** Participants must have received no more than 3 total prior systemic treatment regimens in the advanced or metastatic setting and must have evidence of progression on or after the last treatment regimen received and within 6 months prior to study enrollment.
 - iv) For enrollment in escalation cohorts, participants must have received and progressed on or after anti-PD-(L)1 therapy, if available.
 - v) Participants must have received prior systemic treatment regimens in the advanced or metastatic setting and must have evidence of progression on or after the last treatment regimen received and within 6 months prior to study enrollment.
- g) Participants with NSCLC
 - i) Histologically confirmed NSCLC meeting stage criteria for stage IIIB, stage IV, or recurrent disease.
 - ii) Participants must have recurrent or progressive disease during or after platinum doublet-based chemotherapy or at least two prior lines of systemic therapy for advanced or metastatic disease. OR Must have recurrent or progressive disease within 6 months after completing platinum-based chemotherapy for local disease.
 - iii) **Not applicable per revised protocol 02:** Participants must have known EGFR status, anaplastic lymphoma kinase (ALK) status, and ROS1 receptor tyrosine kinase mutational status.

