 - (a) Participants with an activating EGFR mutation must have received an EGFR tyrosine kinase inhibitor
 - (b) Participants with an ALK translocation or ROS1 mutational status must have received the correspondent targeted therapy
 - iv) For enrollment in escalation cohorts, participants must have received and progressed on or after anti-PD-(L)1 therapy, if available.
 - v) Status for actionable mutations (eg, EGFR, ALK, ROS1, RET, etc.) must be known (when testing is available as per country/region standard of care practices); participants with actionable mutations must have received and progressed on, have been intolerant to, or not be a candidate for, standard tyrosine kinase inhibitors (as available per country/region standard of care practices).
- h) Participants with SCCHN
 - i) Histologically confirmed, recurrent, or metastatic squamous cell carcinoma of the head and neck (oral cavity, pharynx, larynx), and not amenable to local therapy with curative intent.

- ii) Participants who progressed on or after, or were intolerant to, a platinum-containing regimen.
- iii) Prior curative radiation therapy must have been completed at least 4 weeks prior to first study drug administration. Prior focal palliative radiotherapy must have been completed at least 2 weeks before study drug administration.
- iv) Documentation of p16 is sufficient to determine human papillomavirus (HPV) status of tumor for SCCHN of the oropharynx. Note: If results are not available, then a sample (tissue on microscopic slides, tissue block or a fresh tissue biopsy in formalin) should be sent to the central laboratory for analysis.
- v) For enrollment in escalation cohorts, participants must have received and progressed on or after anti-PD-(L)1 therapy, if available.
- vi) For enrollment in the PD cohorts only, participants must have received and been resistant to anti-PD-(L)1 therapy. Refer to inclusion criteria 2 i) for the definition of anti-PD-(L)1 resistance.
- i) Participants with SCCHN in the PD cohorts must have received prior anti-PD-1/PD-L1 therapy and have radiologically or clinically documented disease progression or recurring disease on or within 3 months following last dose of anti-PD-1/PD-L1 therapy for their advanced (metastatic and/or unresectable) cancer, and have been considered for all other potentially efficacious therapies prior to enrollment.
 - (1) One intervening systemic therapy is allowed between anti-PD-(L)1 therapy and enrollment

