- (b) Positive test for qualitative hepatitis C viral load by PCR
- (c) Participants with positive hepatitis C antibody and negative quantitative hepatitis C by PCR are eligible. History of resolved hepatitis A virus infection is not an exclusion criterion.
- (d) Additional testing or substitute testing per institutional guidelines to rule out infection is permitted

l) Evidence of active infection that requires systemic antibacterial, antiviral, or antifungal therapy ≤ 7 days prior to the first dose of study drug (except for viral infections that are presumed to be associated with the underlying tumor type required for study entry).

m) Receipt of non-oncology vaccines containing live virus for prevention of infectious diseases within 30 days prior to first dose of study drug.

n) Any significant acute or chronic medical illness which would interfere with study treatment or follow-up.

o) Any serious or uncontrolled medical disorder that, in the opinion of the investigator, may increase the risk associated with study participation or study drug administration, impair the ability of the participant to receive protocol therapy, or interfere with the interpretation of study results.

p) Previous SARS-CoV-2 infection within 10 days for mild or asymptomatic infections or 20 days for severe/critical illness prior to C1D1.

- i) Acute symptoms must have resolved and based on investigator assessment in consultation with the medical monitor, there are no sequelae that would place the participant at a higher risk of receiving study treatment.

q) Previous SARS-CoV-2 vaccine within 14 days of C1D1.

r) Known HIV positive with an AIDS defining opportunistic infection within the last year or a current CD4 count < 350 cells/ μ L. Participants with HIV are eligible if:

- ◆ they have received antiretroviral therapy (ART) for at least 4 weeks prior to treatment assignment as clinically indicated while enrolled on study
- ◆ they continue on ART as clinically indicated while enrolled on study
- ◆ CD4 counts and viral load are monitored per standard of care by a local health care provider

NOTE: Testing for HIV must be performed at sites where mandated locally.
HIV-positive participants must be excluded where mandated locally.

s) Leptomeningeal metastases

3) Prior/Concomitant Therapy

- a) Cytotoxic agents, unless at least 4 weeks have elapsed from last dose of prior anti-cancer therapy and initiation of study therapy.

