7.7.1 Prohibited and/or Restricted Treatments

The following medications are prohibited during the study (unless utilized to treat a drug-related AE):

- Any live/attenuated vaccine (eg, varicella, zoster, yellow fever, rotavirus, oral polio, and measles, mumps, rubella [MMR]) during treatment and until 100 days post last dose.
- Immunosuppressive agents
- Immunosuppressive doses of systemic corticosteroids (except as stated in [Section 6](#))
- Any concurrent anti-neoplastic therapy (ie, chemotherapy, hormonal therapy, immunotherapy, extensive, non-palliative radiation therapy)
- Any botanical preparation (eg, herbal supplements or traditional Chinese medicines) intended to treat the disease under study or provide supportive care. Use of marijuana and its derivatives for treatment of symptoms related to cancer or cancer treatment are permitted if obtained by medical prescription or if its use (even without a medical prescription) has been legalized locally.
- Administration of investigational SARS-CoV-2 vaccines is not allowed during the study. Participants may receive approved SARS-CoV-2 vaccines while continuing on study treatment at the discretion of the Investigator.
- Treatment of active SARS-CoV-2 infections or high-risk exposures, including use of investigational therapies, is allowed and should be discussed with the medical monitor.

No concomitant medications (prescription, over-the-counter, or herbal) are to be administered during study unless they are prescribed for treatment of specific clinical events. Any concomitant therapies must be recorded on the CRF.

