7.7.3.1 Radiotherapy

Palliative and supportive care for disease-related symptoms may be offered to all participants on the trial; however, Investigators should consult with the BMS Medical Monitor prior to initiating palliative radiation in participants who have not yet completed the DLT evaluation interval (Parts 1A, 1B, and 1C).

The potential for overlapping toxicities with radiotherapy and BMS-986315 administered as monotherapy or in combination with nivolumab or cetuximab is currently not known. Therefore, palliative radiotherapy is not recommended while receiving any of these drugs, alone or in combination. If palliative radiotherapy in short courses and for isolated fields is required to control symptoms not clearly related to disease progression, then drug administration should be withheld,

if possible, for at least 1 week before radiation and for at least 1 week after its completion. Participants should be closely monitored for any potential toxicity during and after receiving radiotherapy. Prior to resuming study drug treatment, radiotherapy-related AEs should resolve to \leq Grade 1 or baseline and participants must meet relevant eligibility criteria as determined by the BMS Medical Monitor in discussion with the Investigator. The BMS Medical Monitor must be consulted prior to re-initiating treatment in a participant with a dosing interruption lasting > 8 weeks after the last dose.

Details of palliative radiotherapy should be documented in the source records and eCRF. Details in the source records should include: dates of treatment, anatomical site, dose administered and fractionation schedule, and AEs. Symptoms requiring palliative radiotherapy should be evaluated for objective evidence of disease progression. Participants receiving palliative radiation of target lesions will have the evaluation of BOR just prior to radiotherapy but such participants will no longer be evaluable for determination of response subsequent to the date palliative radiation occurs.

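### Outside the brain, NSCLC and RCC participants in Part 1A and 1B escalation have no pre-dose radiotherapy interval, while SCCHN participants do; one rule should cover all three (low severity)

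*Combined protocol and SAP*

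**What the plan says.** **Eligibility.** Section 6.1, criterion 2 h) iii, under the SCCHN heading, requires 4 weeks after curative radiotherapy and adds: "Prior focal palliative radiotherapy must have been completed at least 2 weeks before study drug administration". The RCC list (2 f) and the NSCLC list (2 g) have no radiotherapy item. Criterion 2 d) covers brain metastases in every tumor type and asks for "no radiographic progression for at least 4 weeks following radiation and/or surgical treatment". In Section 6.2, exclusion 3 a) concerns "Cytotoxic agents, unless at least 4 weeks have elapsed from last dose of prior anti-cancer therapy and initiation of study therapy"; 3 b) and 3 c) set similar washouts for non-cytotoxic agents and immune therapy, in weeks or half-lives.

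**Radiotherapy on study.** Section 7.7.1 prohibits "extensive, non-palliative radiation therapy" during the study. Section 7.7.3.1 says that "Investigators should consult with the BMS Medical Monitor prior to initiating palliative radiation in participants who have not yet completed the DLT evaluation interval". It states that the potential for overlapping toxicity with the study drugs is not known. It asks that drug be withheld, if possible, "for at least 1 week before radiation and for at least 1 week after its completion", and that radiotherapy-related AEs return to Grade 1 or less, or to baseline, before dosing resumes. None of this depends on tumor type.

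**DLTs.** Section 5.1.3 defines DLTs "excluding toxicities clearly related to disease progression or intercurrent illness". The catch-all in Section 5.1.3.4 says that other Grade 3 or higher events, "excluding toxicities clearly related to disease progression or intercurrent illness, will be considered a DLT", and then lists eight Grade 3 exceptions.

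**Who enters where.** Section 5.4.4 places SCCHN, NSCLC and RCC in escalation. Part 1C (Section 5.1) and all PD cohorts (Section 5.1.2.4) are SCCHN only.

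**The concern.** Take two participants who finished focal palliative radiotherapy to a site outside the brain 5 days before C1D1. The one with SCCHN is ineligible. The one with NSCLC or RCC may be dosed, with no interval to observe. The protocol gives no reason for the difference, and Section 7.7.3.1 is more cautious about the same exposure once a participant is on treatment.

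Two things are at stake. The first is the safety of a participant who receives a first-in-human antibody shortly after irradiation. The second is attribution: a radiation toxicity that appears or worsens in the 28-day window may be hard to separate from drug toxicity. If it is counted as a DLT, it enters a decision that rests on 2 to 4 people, and under Section 5.1.3 the participant receives no further study drug.

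**Working it through.** **1. The rules side by side**

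| Rule before C1D1 | SCCHN | NSCLC | RCC |
|---|---|---|---|
| Brain radiotherapy (2 d) | 4 weeks without progression | same | same |
| Curative, outside brain | 4 weeks | none | none |
| Focal palliative, outside brain | 2 weeks | none | none |
| Radiotherapy toxicity resolved | not stated | not stated | not stated |

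Section 7.7.3.1 asks for a post-radiotherapy hold and for resolution, but only before dosing resumes. Exclusions 3 a) and 3 b) refer to prior anti-cancer therapy, but they govern agents with a last dose or a half-life. Reading either as a 4-week radiotherapy washout would contradict the 2 weeks allowed in SCCHN.

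**2. Who is exposed** (Sections 5.2 and 10.1)

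- SCCHN-only places: Part 1C 116 + Part 1A PD cohort 40 + Part 1B PD cohorts 80 = 236; 236/308 = 76.6%.
- Remainder: 308 − 236 = 72 = 36 (Part 1A escalation) + 36 (Part 1B escalation).
- SCCHN participants also use these 72 places. Neither the tumor split nor the rate of recent radiotherapy is given, so 72 is a ceiling and not an estimate.

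**3. Which events could be counted**

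- Removed as Grade 3 exceptions (5.1.3.4): among others, tumor flare, which covers pain, irritation or rash at tumor sites; fatigue of 7 days or less; and nausea, vomiting or diarrhea under 48 hours.
- Removed unless drug-related (5.1.3.4): Grade 3 or higher pneumonitis, bronchospasm, uveitis and neurologic toxicity.
- Removed because not an AE (Appendix 3): stable toxicity already present before dosing, since an AE must be new or a worsening.
- Left, with no radiotherapy carve-out: Grade 4 hematologic events (5.1.3.2); Grade 4 skin toxicity and Grade 3 rash that persists after an infusion delay (5.1.3.3); Grade 2 pneumonitis that does not respond within 14 days to delay and steroids; and other Grade 3 or higher events outside the exceptions (5.1.3.4).

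**4. The plan's boundaries reproduced** (Section 10.1.1: target 30%, escalate 23.6%, de-escalate 35.9%)

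The documents do not state the BOIN alternatives. I assume the defaults φ₁ = 0.6φ = 0.18 and φ₂ = 1.4φ = 0.42, with φ = 0.30.

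- λe = ln[(1−φ₁)/(1−φ)] / ln[φ(1−φ₁)/(φ₁(1−φ))] = ln(0.82/0.70) / ln(0.246/0.126) = 0.2365
- λd = ln[(1−φ)/(1−φ₂)] / ln[φ₂(1−φ)/(φ(1−φ₂))] = ln(0.70/0.58) / ln(0.294/0.174) = 0.3585

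Both agree with the plan.

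**5. Effect of one wrongly counted DLT** (Appendix 8, Table 1; no data pending)

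| Treated | True count | With one extra DLT |
|---|---|---|
| 2 | 0/2: Escalate | 1/2 = 50%: De-escalate |
| 3 | 0/3: Escalate | 1/3 = 33.3%: Stay |
| 4 | 0/4: Escalate | 1/4 = 25%: Stay |

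- A cohort of 2 is possible only at 80 and 200 mg in Part 1A (Section 10.1.1). At 80 mg, De-escalate means treating again at 80 mg (Appendix 8, note b).
- At 1/3 with one participant pending, the table says De-escalate if STFT ≤ 0.88, that is 0.88 × 28 = 24.6 days of follow-up.
- Five treated with 1 DLT and none pending is Escalate. Recovery after Stay therefore needs at least 5 − 3 = 2, or 5 − 4 = 1, further DLT-free participants.

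**6. Illustration only.** Assume a true DLT rate of 10%, a cohort of 3, and one recently irradiated member with extra probability q of a counted radiation event. Then P(0 of 3) = 0.9³(1 − q) = 0.729(1 − q): 0.729, 0.693, 0.656 and 0.583 for q = 0, 0.05, 0.10 and 0.20. The documents supply none of these inputs.

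**The case against.** The strongest case against is that the DLT consequence is thin.

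- The Grade 3 exceptions and drug-related qualifiers remove much of what focal radiotherapy might plausibly cause at a tumor site.
- Screening records toxicities of earlier treatment, and signs and symptoms within 14 days before dosing (Table 2-1). Exclusions 2 n) and 2 o) let the investigator turn away a participant whose condition would interfere with treatment or interpretation.
- Potential DLTs lead to a drug hold while relatedness is assessed (5.1.3, 7.4.1). Appendix 3 requires alternative causes to be considered.
- The consultation rule in 7.7.3.1 can be read to include consented participants still in screening. The clearest uncovered case is then a course that ended before consent, followed by dosing within 14 days.
- Table 1 guides decisions and does not dictate them; clinical assessment weighs all available data (10.1.1).
- Tumor-specific eligibility lists are a legitimate choice.

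Most of this stands, and it sets the severity. It does not close the gap. None of these provisions sets an interval, and consultation about radiotherapy yet to start does not reach a course already finished. Relatedness review works only when the cause can be told apart, which an interval makes easier.

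A reader might infer that any radiation toxicity in the window becomes a DLT, or that the MTD will be biased downward. The documents do not support either: the filters in 5.1.3.4 and the AE definition remove many events, and no frequency can be derived. A reader might also infer that NSCLC and RCC participants have no radiotherapy protection at all. Criterion 2 d), Section 7.7.1 and the consultation rule show otherwise.

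**Conclusion.** The gap is real and small. Outside the brain rule, NSCLC and RCC participants in Part 1A and 1B escalation have no radiotherapy-to-first-dose interval. They also have no stated requirement that radiotherapy toxicity resolve before C1D1; SCCHN shares that second omission. The exposure that matters is mainly focal palliative radiotherapy ending less than 14 days before C1D1. Curative courses should be rare here, because these participants must have advanced, recurrent or progressive disease after systemic therapy.

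The consequence is a residual set of new, severe or persistent radiation toxicities that could be counted as a DLT. The number affected is unknown and is at most the NSCLC/RCC share of 72 slots. The error is conservative: extra participants at a dose, or a dose set too low. The Table 1 shifts show what one miscounted event does, not how likely it is. This is a harmonization point of low severity.

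**What to change.** Move the 2-week focal palliative interval from 2 h) iii to the criteria common to all three tumor types, and the 4-week curative interval with it for consistency. The palliative interval is the part that matters. If the sponsor wants NSCLC and RCC treated differently, the protocol should say why. The interval does not itself require toxicity to resolve; repeating the resolution condition of Section 7.7.3.1 at C1D1 would cover that as well.

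The change needs an amendment with ethics approval. A few NSCLC or RCC participants would wait up to 2 weeks (palliative) or 4 weeks (curative). Within the 35-day screening period, palliative radiotherapy ending by day 35 − 14 = 21 still fits, and curative radiotherapy ending by day 35 − 28 = 7. Later completion may require re-enrollment under Section 6.4.1, since the re-consent route in Section 5.1.1 is worded for overruns caused by study-related procedures. Some participants may need repeat baseline imaging, because body scans must fall within 28 days before first dose (Table 2-1).
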